7.7.3 Laboratory Evaluations

Data for the following hematology, serum chemistry, lipid panel, and urinalysis analytes received from central laboratory will be listed and summarized by treatment group and visit. If data for any additional analytes are also received, then these will be listed only.

Hematology	Serum Chemistry	Urinalysis
Complete blood count (CBC) with differential Platelet count	Albumin Alkaline phosphatase Alanine transaminase (ALT) Amylase Aspartate transaminase (AST) Total bilirubin Glucose Blood urea nitrogen (BUN) Calcium Carbon dioxide Chloride Creatinine Magnesium Phosphorus Potassium Sodium Total protein Uric acid	Appearance Color Glucose Ketones Nitrite pH Protein Specific gravity Occult blood Leukocyte esterase Bilirubin Urobilinogen Urine microscopy White Blood Cell Red blood Cell Epithelial cells Bacteria Casts Crystals
Lipid panel	Other Samples	
High-density lipoprotein (HDL) Low-density lipoprotein (LDL) Total cholesterol Triglycerides Creatinine phosphokinase (CPK)	Pregnancy tests (females only) Urine screen (drugs of abuse and THC)	

All laboratory data will be reported in International System of Units and conventional units. Out-of-reference-range values will be flagged as high (H) or low (L) in the listings.

For analysis purposes, values preceded by a "<" or a ">" sign (ie, those below or above the limits of quantification) will be considered equal to the lower or upper limit of quantification, respectively.

Laboratory data will be summarized by visit using standard descriptive statistics by treatment group and overall for the Safety population. Changes from Baseline will also be summarized.

For hematology and serum chemistry, shift tables presenting movement in and out of reference range from Baseline to each scheduled post-Baseline visit will be provided by treatment group and overall for the Safety population. Percentages will be based on the number of patients with both non-missing Baseline and relevant post-Baseline results.

For each laboratory analyte, the Baseline value will be defined as last scheduled or unscheduled value collected prior to the first dose of study drug during the double-blind Treatment Period. Assessments carried out on the day of first study drug administration are considered to have taken place before the study drug administration, if the corresponding times have not been recorded.

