Safety analyses, based on the Safety Population, will involve examination of the descriptive statistics and individual patient listings for any effects of study treatment on clinical tolerability and safety. Summaries will be prepared by treatment group (ie, placebo and LX9211 dose level) and, by study visit where applicable. The incidence of AEs will be presented by severity and by relatedness as assessed by the Investigator. All safety data will be provided in listings.

Treatment-emergent adverse event (TEAE) summaries will include the overall incidence of TEAEs, Incidence of TEAEs (by System Organ Class [SOC] and Preferred Term [PT]), TEAEs by maximum intensity, TEAEs by relationship to study treatment, events leading to discontinuation of study drug, deaths, and SAEs.

Vital signs, ECGs findings, PE findings, clinically significant PE findings, weight, and laboratory parameters (chemistry, hematology, and urinalysis) will be summarized descriptively at each time point. Actual and change from Baseline data will be calculated and summarized. In addition, shift table analyses will be presented for the laboratory data.

Table of Contents

1.	Syn	opsis		3
2.			eviations and Definitions of Terms	
3.	3.1		round on LX9211 and Neuropathic Pain	
	3.2	_	1 Nonclinical Pharmacology, Pharmacodynamics, and Toxicology	
		3.2.1	In Vitro Pharmacodynamic Studies	2 €
		3.2.2	In Vivo Pharmacodynamic Studies	
		3.2.3	Safety Pharmacology	
		3.2.4	Summary of Pharmacology	
		3.2.5	LX9211 Toxicology	
		3.2.6	Preclinical GLP-Compliant Toxicology Studies in Rats	28
		3.2.7	Preclinical GLP-Compliant Toxicology Studies in Dogs	
		3.2.8	Embryo-Fetal Development Study in Rats	30
		3.2.9	Embryo-Fetal Development Study in Rabbits	30
	3.3	Clinica	al Trials of LX9211 in Humans	31
	3.4	Ration	ale for Current Study	32
		3.4.1	Rationale for Selection of Dose	32
	3.5	Ration	ale for Study Design and Control Groups	33
4.	Stuc	ly Objec	tives	33
	4.1	Primar	y Objective	33
	4.2	Second	dary Objective(s)	33
	4.3	Other 0	Objective(s)	33
5.	Inve	stigation	nal Plan	34
	5.1	Overal	1 Study Design	34
Figu	re 5.1	−1 Tre	eatment Schema	35
		5.1.1	Screening Period	36
		5.1.2	Run-in Period	36
		5.1.3	Randomization/Treatment Period	36
		5.1.4	Safety Follow-up Period	
		5.1.5	Optional Substudies.	
6.		-	ation	
	6.1			
	6.2		ion Criteria	
	6.3	Criteri	a for Stopping Treatment/Study Withdrawal	
		6.3.1	Lost to Follow-up	43

	6.4	Criteri	a for Term	ination of the Study	43

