9.1.1.1 Special considerations for bladder dysfunction-related adverse events

In studies with LX9211 in dogs, changes to the urinary bladder (including minimal inflammation, slight urothelial hyperplasia, minimal focal ulceration, and minimal muscle degeneration) were noted. The doses used in these animal studies were much higher than what will be used in this Phase 2. In the Phase 1 SAD and MAD studies with LX9211, no clinically significant CMP, UA findings, or bladder dysfunction-related AEs were reported in any subject.

In this study, bladder dysfunction-related AEs will be closely monitored on an ongoing basis. In addition, an unscheduled visit may be conducted in case of a reported AE suspicious for urinary bladder abnormalities, where additional labs and follow-up may be obtained, as deemed necessary.

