10.4.5.3 Clinical Laboratory Parameters

Laboratory results will be reported in Conventional units and Systeme International (SI). Clinical laboratory value observed at Baseline (predose), at each time point, and changes from Baseline to each assessment time point will be summarized using descriptive statistics and presented by treatment group. Additionally, each patient's laboratory results will also be classified into Low, Normal, and High according to standard normal ranges and summarized using shift tables, comparing the Baseline and each assessment time point. Percentages will be based on the

number of patients with both non-missing baseline and relevant postbaseline results. A by-patient data listing of all clinical laboratory test results will be provided.

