10.4.5.6 Electrocardiogram (ECG)

The actual values of the 12-lead ECG parameters at Baseline, at each time point, and change from Baseline will be summarized using descriptive statistics. The number and percentage of patients with at least 1 post Baseline abnormal ECG result will be summarized using descriptive statistics and presented by treatment group.

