6.1.2 Secondary efficacy and other efficacy endpoints based on data collected at clinic visits

The rest of the efficacy endpoints based on data collected at clinic visits will follow the visit windows defined in [Table 1.2](#).

Table 1.2 Definition of visit windows for efficacy data collected at each visit

Visit	Target Day of Visit ^a	Acceptable visit window
Screening	Day -28	NA
Run-in ^b	Day -14	NA
Baseline	Day 1	Day 1 to Day 4
Week 2	Day 15	Day 5 to Day 22
Week 4	Day 29	Day 23 to Day 36
Week 6	Day 43	Day 37 to Day 60
Week 11	Day 78	Day 61 to 35 days after the last treatment dose during the double-blind Treatment Period

^a relative to the date of first dose of study drug during the double-blind Treatment Period/date of Randomization/date of Baseline Visit (Day 1)

^b weight is collected

In general, the Baseline value for a variable is defined the last value collected or taken on or before Day 1 and prior to the first dose of double-blind study drug. In cases where there are multiple such values, the non-missing value closest to the start of study treatment is selected. If time is available for an assessment on Day 1, it will be compared with dosing time on Day 1 to define the Baseline value.

Multiple visits within the same window will be dealt with as follows:

- If both scheduled and unscheduled visits fall within the same visit window, the scheduled visit will be used for analysis.
- If multiple scheduled visits occur within a single visit window, then the visit closest to the target day of the visit window will be used in the analysis. If there is a tie, the later visit will be used in the analysis.

- If multiple unscheduled visits occur within a single visit window (with no scheduled visit within the window) then the unscheduled visit closest to the target day of the visit window will be used in the analysis. If there is a tie, the later unscheduled visit will be used in the analysis.

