7.7.5 Electrocardiograms

The following quantitative ECG measurements will be taken during the study:

- Heart rate (beats/min)
- PR interval (msec)
- QRS duration (msec)
- QT interval (msec)
- QTc interval (msec)
- Fridericia corrected QT (QTcF) interval (msec)
- RR interval (msec)

The ECG measurements and changes from Baseline in ECG will be listed and summarized by visit using standard descriptive statistics by treatment group and overall for the Safety population.

The Baseline value will be defined as last scheduled or unscheduled value collected prior to the first dose of study drug during the double-blind Treatment Period. Assessments carried out on the day of first study drug administration are considered to have taken place before the study drug administration, if the corresponding times have not been recorded.

An overall Investigator assessment of ECG will be provided (categories "normal", "abnormal, not clinically significant", "abnormal, clinically significant", "indeterminate", "not evaluable", and "unknown").

The Investigator assessment will be listed and the number and percentage of patients within each assessment category will be tabulated by visit, treatment group and overall for the Safety population. Shifts from Baseline (normal vs. abnormal, not clinically significant vs. abnormal, clinically significant) at each post-Baseline visit will be presented by treatment group and overall for the Safety population.

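### The SAP omits, without declaring it, two safety summaries that the protocol promises: patients per arm with any post-Baseline abnormal ECG, and shift tables for urinalysis and the lipid panel

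*SAP*

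**What the plan says.** **ECG.** Protocol 10.4.5.6 commits to a patient-level count by treatment group: "The number and percentage of patients with at least 1 post Baseline abnormal ECG result will be summarized". SAP 7.7.5 classifies each ECG by the investigator's overall assessment, and "the number and percentage of patients within each assessment category will be tabulated by visit, treatment group and overall". It adds shifts from Baseline at each visit, descriptive statistics for the ECG intervals (QTc and QTcF among them) and a listing. No row counts a patient once across visits.

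**Laboratory.** The protocol synopsis, under Safety Data Analysis, states that "laboratory parameters (chemistry, hematology, and urinalysis) will be summarized descriptively at each time point" and continues: "In addition, shift table analyses will be presented for the laboratory data". Protocol 10.4.5.3 says of each patient that "laboratory results will also be classified into Low, Normal, and High according to standard normal ranges and summarized using shift tables", setting Baseline against each time point. Neither place excludes a panel. SAP 7.7.3 names four groups to be listed and summarized by visit (hematology, serum chemistry, lipid panel, urinalysis), then gives shift tables to two: "For hematology and serum chemistry, shift tables presenting movement in and out of reference range from Baseline to each scheduled post-Baseline visit".

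**Windows.** SAP 6.1.3 applies the visit windows of Table 1.2 to laboratory and ECG data. One of the rules in 6.1.2 reads: "If both scheduled and unscheduled visits fall within the same visit window, the scheduled visit will be used for analysis".

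**Declared changes.** SAP Section 8 lists one, the switch from MMRM to ANCOVA for NPSI.

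**The concern.** Protocol 10.4 says the SAP will add detail to the methods, so a reader would expect both summaries to survive, or a stated reason if they do not. The basic ECG safety question is how many patients in each arm ever had an abnormal tracing on study. The protocol chose that count, and no table in SAP 7.7.5 answers it.

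For urinalysis, what goes missing is the number of patients who moved from normal at Baseline to abnormal at each visit. That display has some interest here, because protocol 9.1.1.1 reports urinary bladder changes in dogs and says that "bladder dysfunction-related AEs will be closely monitored on an ongoing basis".

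An undeclared omission also cannot be told apart, later on, from an oversight or a choice.

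**Working it through.** The plan gives no figure on this point, so the check compares the texts and asks what the by-visit tables can recover.

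**1. ECG occasions.** After Day 1, the schedule of events (protocol Appendix A) has ECGs at Week 6 or end of treatment/early withdrawal, and at Week 11 or 35 days after end of treatment/early withdrawal.

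**2. Can the protocol's count be derived from by-visit counts?** Let *a* patients in an arm be abnormal at Week 6 and *b* at Week 11. They may be the same or different patients, so max(*a*, *b*) ≤ number ever abnormal ≤ *a* + *b*. Take 94 patients per arm (protocol 10.1) and hypothetical counts, since the documents give no expected rate:

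- *a* = *b* = 3: from 3/94 = 3.2% to 6/94 = 6.4%.
- *a* = *b* = 5: from 5/94 = 5.3% to 10/94 = 10.6%.

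With equal counts the upper bound is twice the lower, and the tables cannot say where the truth lies.

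**3. What the windows do.** Table 1.2 assigns Days 5–22 to Week 2, 23–36 to Week 4, 37–60 to Week 6, and Day 61 onward to Week 11.

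- An unscheduled ECG is set aside when a scheduled one lies in the same window. If only the unscheduled one is abnormal, the patient appears as normal in that row.
- An early-withdrawal ECG on Days 5–36 goes to Week 2 or Week 4, where no ECG is planned for patients who continue.
- A follow-up ECG 35 days after a last dose on Day *d* falls on Day *d* + 35. For *d* = 2 this is Day 37, and for *d* = 25 it is Day 60. An off-drug ECG after a last dose on about Days 2–25 can therefore land in the Week 6 row. The range is approximate because the follow-up visit has a +7 day window.

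Example: last dose on Day 20, abnormal early-withdrawal ECG on Day 21, normal follow-up ECG on Day 20 + 35 = 55. The patient is abnormal in the Week 2 row and normal, off drug, in the Week 6 row. A count over all post-dose ECGs does not depend on this placement.

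**4. Laboratory panels.** Urinalysis is covered by the protocol's promise because the synopsis names it as laboratory data. The lipid panel is covered because 10.4.5.3 excludes nothing. The SAP lists that panel, which includes CPK, apart from serum chemistry, so its shift-table sentence does not reach it. The promised shift table is itself by time point. What is lost is movement between categories from Baseline to each visit, not an ever-abnormal count.

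**The case against.** The best defence is that little information disappears. Safety analysis in this Phase 2 trial is descriptive, with no formal tests (protocol 10.4.5). Out-of-range laboratory values are flagged in the listings, and the ECG assessments are listed. Protocol 8.1.1 and 9.1.1 direct clinically significant laboratory findings to adverse event reporting, and SAP 7.7.2 counts patients with each event by arm. Early-withdrawal ECGs are not discarded either. SAP 7.7.5, unlike 7.7.3, does not confine itself to scheduled visits, so on its wording they would appear in Week 2 or Week 4 rows. Low/Normal/High also suits dipstick items poorly, and microscopy is done only when certain dipstick findings are present (protocol 8.1.1), so many patients would lack the microscopy baseline that a shift needs.

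All of that stands, and it limits the point. It does not supply the missing summaries. A listing is not a count by arm, adverse event reporting of laboratory findings depends largely on the investigator's view of clinical significance, and by-visit rows do not add up to patients.

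Four stronger readings are tempting, and the documents do not support them:

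- *A patient with a bladder problem found at an extra visit is counted nowhere.* The unscheduled visit in protocol 9.1.1.1 follows a reported adverse event, which the adverse event tables count by arm.
- *QT risk goes unsummarized.* SAP 7.7.5 keeps QTc and QTcF values and changes by visit. The lost count covers any abnormal ECG, not QT specifically. Protocol 3.2.3 attributes no dog cardiovascular effect clearly to the drug, and 9.3.2 defines no adverse event of special interest.
- *The planned 20% dropout measures how many patients' ECGs fall outside the Week 6 row.* It does not. Withdrawals on Days 37–60 stay in that window, and some follow-up ECGs of early withdrawals enter it.
- *Restoring the laboratory shift tables would show who was ever abnormal.* By step 4 of the working, it would not.

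**Conclusion.** Two protocol-specified safety summaries are absent from the SAP, and Section 8 declares neither. The ECG omission is material: the protocol's count cannot be recovered from the planned tables, and the window rules blur the rows that remain. The laboratory omission is smaller, a loss of category shifts for urinalysis and lipids while listings and by-visit summaries stay. In both cases the trial loses systematic counts by arm, not all patient-level information. Efficacy conclusions are unaffected.

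This rests on the SAP text alone. The SAP refers to table shells that are not among the documents, and those could carry the missing displays. The lipid part also assumes that the SAP means what its own list says, that lipids are separate from serum chemistry. The 5 and 3 per visit are illustrations, not forecasts.

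**What to change.** - **SAP 7.7.5:** reinstate the number and percentage of patients per arm with at least one post-Baseline abnormal ECG. Use all ECGs after the first double-blind dose, including unscheduled and early-withdrawal ECGs, regardless of window. State which investigator categories count as abnormal.
- **SAP 7.7.3:** extend the shift tables to urinalysis, with normal/abnormal categories for dipstick items, and to the lipid panel.
- Keep the by-visit tables as planned.
- If either summary is left out on purpose, record that with the reason in SAP Section 8.

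The data are already collected, so the cost is SAP wording and a few tables. One footnote is needed: retested patients contribute more assessments, and so have more chances of an abnormal ECG.

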7.7.4 Vital Signs

The following vital signs and weight (kg) will be listed and summarized by treatment group and visit.

- Systolic and diastolic BP (mm Hg)
- Pulse rate (beats/min [BPM])
- Respiration rate (breaths/min)
- Body temperature (°C)

Vital signs and weight data and changes from Baseline in vital signs and weight will be summarized by visit using standard descriptive statistics by treatment group and overall for the Safety population. The Baseline value will be defined as last scheduled or unscheduled value collected prior to the first dose of study drug during the double-blind Treatment Period. Assessments carried out on the day of first study drug administration are considered to have taken place before the study drug administration, if the corresponding times have not been recorded.

In addition, for vital signs, shift from Baseline (normal vs. abnormal, not clinically significant vs. abnormal, clinically significant) at each post-Baseline visit will be provided by treatment group and overall for the Safety population.

7.7.5 Electrocardiograms

The following quantitative ECG measurements will be taken during the study:

- Heart rate (beats/min)
- PR interval (msec)
- QRS duration (msec)
- QT interval (msec)
- QTc interval (msec)
- Fridericia corrected QT (QTcF) interval (msec)
- RR interval (msec)

The ECG measurements and changes from Baseline in ECG will be listed and summarized by visit using standard descriptive statistics by treatment group and overall for the Safety population.

The Baseline value will be defined as last scheduled or unscheduled value collected prior to the first dose of study drug during the double-blind Treatment Period. Assessments carried out on the day of first study drug administration are considered to have taken place before the study drug administration, if the corresponding times have not been recorded.

An overall Investigator assessment of ECG will be provided (categories "normal", "abnormal, not clinically significant", "abnormal, clinically significant", "indeterminate", "not evaluable", and "unknown").

The Investigator assessment will be listed and the number and percentage of patients within each assessment category will be tabulated by visit, treatment group and overall for the Safety population. Shifts from Baseline (normal vs. abnormal, not clinically significant vs. abnormal, clinically significant) at each post-Baseline visit will be presented by treatment group and overall for the Safety population.

7.7.6 Physical Examination

Physical examination results (normal/abnormal) and details of abnormalities will be listed for each patient.

7.8 Interim Analysis

Enrollment will not be temporarily halted while data for the interim analysis is being reviewed.

An interim analysis of the primary endpoint will be performed to test for futility when approximately 50% of the planned information has been achieved. This will occur when the first 141 patients have been accrued and followed to endpoint at Week 6 or dropped out from the trial earlier, whichever event occurs first. Should a patient drop out early in the study, but return for the Week 6 visit, the Week 6 data will be used in the analysis.

To maintain continuous blinding and study integrity, analysis will be conducted by a separate unblinded team. Details of the unblinding process for the interim analysis and the resulting controlled dissemination of interim analysis data will be detailed in the Data Monitoring Committee (DMC) Charter document.

A non-binding futility boundary will be used to test treatment group differences in the primary endpoint at 50% of the original planned information. The set of boundary values will be derived by using a beta spending function and specification of a power family with value = 3.672. The monitoring boundary is constructed by assuming a 1-sided test with a per comparison Type I error rate = 0.0141, assuring an overall $\alpha = 0.025$ (or a two-sided $\alpha = 0.05$) for the two LX9211 versus placebo comparisons. Use of this beta spending function for futility testing is conservative and results in cumulative beta error rates of 0.015 and 0.197 at the interim and final analyses, respectively. Application of the futility analysis is to serve as a guideline and is not the only source of information used to evaluate the trial for a negative finding. Assessment of other data available at the interim analysis will be used to qualify the trial for a recommendation of futility (eg, secondary and other efficacy variables, safety data).

In addition to the above planned interim analysis, meetings for an independent DMC data reviews will be scheduled to ensure proper safety assessment during enrollment and study conduct. Initially, proposed timelines for meeting frequency to review unblinded safety data will be based on fractions of patient accrual (eg, 25% and 75% of the sample size). A final DMC meeting is planned when the study completes. The DMC will develop a charter and establish criteria when meetings are to occur, plus identify a time for the planned interim analysis should this latter event fall outside the times of the reoccurring meetings. The DMC review meetings will occur until database lock or at an earlier time deemed suitable by the DMC. This meeting schedule may be modified based on the observed patient accrual rates or signals seen in the safety data. DMC members will also receive unblinded

summaries of serious adverse events on a monthly basis to review potential emerging safety trends.

8. Changes in Planned Analysis

For NPSI, an ANCOVA model will be used to evaluate the treatment effect instead of a MMRM since the statistical analysis is conducted for the change scores at Week 6 only.

9. Data Issues

Not applicable.

10. References

Cleeland CS The Brief Pain Inventory User Guide 1991

11. Appendices

